#### **11. Subject Safety and Data Monitoring**

All study records will be identified by a study identification number. [REDACTED]

**12. Procedures to Maintain Confidentiality:**

All study records and information will be identified by the subject number. All subject identifiers will be removed from all documents. The link between subject name and study ID number will be kept in separate password-protected files. [REDACTED]

[REDACTED] All electronic study data will be password protected with access limited to members of the research team. Electronic data will be password protected.

[REDACTED]

[REDACTED]

[REDACTED]

[REDACTED]

[REDACTED]

[REDACTED]

**14. Biostatistics:**

The primary outcome of this study is the VSQ. We have estimated the standard deviation to be 2.5 based on prediction of pre-treatment scores ranging from 4 to 14. To detect a difference of 3 points on this measure with 80% power, 20 subjects per group will be required.

One way analysis of variance will be used for comparison of groups both for the VSQ and the Q-PCR data. Questionnaire results will be compared by comparing the results at each time point compared to pretreatment assessment.

UT Southwestern affiliated clinical statisticians have been and will continue to be consulted throughout the statistical analysis process.

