## Treatment Groups

*IntraGen:* █ patients will each undergo a three-part treatment of the vulvovaginal area. █

*IntraGen Placebo:* █ patients will undergo a three-part placebo treatment, space 1 month apart (+/- 10 days) of the vulvovaginal area. █

[figure not shown]
DiVa: █ patients will undergo a three-part treatment, spaced 1 month apart (+/- 10 days) of the vulvovaginal area. █

DiVa Placebo: █ patients will undergo a three-part placebo treatment, spaced 1 month apart (+/- 10 days) of the vulvovaginal area. █

[figure not shown]
All

[figure not shown]
Each patient will undergo testing at baseline and will be followed conservatively with no further therapy until they reach 6 months (+/- 10 days) █

[figure not shown]
█ Those in the treatment group will be followed to 9 months (+/- 10 days) after the initiation of treatment with appropriate analysis. Those in the placebo group will be provided 3 monthly treatments with both █ RF and █ HFL .These post placebo dual therapy patients will be conservatively followed with no further treatment until they reach 6 months (+/- 10 days) after the initiation of the dual █ RF and █ HFL treatments. 6 months (+/- 10 days) post dual therapy they will return for subjective and objective testing. These patients will return for 9 month visit (+/- 10 days) after the initiation of dual therapy. P █

[figure not shown]

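### Do the printed sample-size inputs for the VSQ contradict the figure of 20 subjects per group?

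*Combined protocol and SAP*

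**What the plan says.** Section 14 names the VSQ as the primary outcome. On variability it says "We have estimated the standard deviation to be 2.5 based on prediction of pre-treatment scores ranging from 4 to 14", and it then gives the size: "To detect a difference of 3 points on this measure with 80% power, 20 subjects per group will be required". The analysis follows: "One way analysis of variance will be used for comparison of groups both for the VSQ and the Q-PCR data". A further sentence deals with change over time: "Questionnaire results will be compared by comparing the results at each time point compared to pretreatment assessment".

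The visible text of Section 14 gives no alpha or sidedness, number of groups in the comparison, pattern of means, dropout or multiplicity allowance, or pre/post correlation. No blacked-out text is visible inside that section.

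Treatment Groups (Section 4) lists four arms: IntraGen, DiVa and a placebo arm for each. All four arm sizes are blacked out. The follow-up text there uses the singular: "Those in the treatment group will be followed to 9 months (+/- 10 days) after the initiation of treatment with appropriate analysis", and "Those in the placebo group will be provided 3 monthly treatments with both" RF and HFL.

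**The concern.** A sample-size statement should be reproducible from its own inputs. Entered into the usual formulae at the conventional alpha, SD 2.5, difference 3 and power 80% give a number clearly below 20 whether two, three or four groups are compared. The reader cannot tell which comparison the 80% belongs to, and the singular wording about treatment and placebo groups adds some doubt about how many groups are meant.

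The SD raises a second doubt. It comes from a predicted spread of pre-treatment scores, so it describes one score at one visit. If the ANOVA were run on change from pretreatment, the relevant SD would depend on a correlation that the plan does not give, and 20 per group could then be too few. The protocol's hypothesis is that the benefit may be a placebo effect, so a null between-group result is a real possibility and the power behind it matters.

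**Working it through.** **Inputs.** From Section 14: SD 2.5, difference 3 (standardised 3/2.5 = 1.2), power 80%, 20 per group. Assumed, because not printed: two-sided alpha 0.05, equal groups, no allowance, a single score. The SD itself reproduces as a quarter of the predicted range: (14 − 4)/4 = 2.5.

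**Two groups.** By the normal approximation, n = 2(1.96 + 0.8416)² × 2.5²/3² = 2 × 7.849 × 6.25/9 = 10.9, so 11. With the noncentral t distribution, power is 0.763 at n = 11 and 0.802 at n = 12, so 12.

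**One-way ANOVA, k groups.** The noncentrality is λ = n Σ(μᵢ − μ̄)²/SD² on k − 1 and k(n − 1) degrees of freedom. If the largest difference is 3, the least favourable pattern puts the remaining means midway, so Σ = 2 × 1.5² = 4.5 and λ = n × 4.5/6.25 = 0.72n. At n = 20, λ = 14.4.

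| Groups | Power just below | n for 80% | Power at n = 20 | Difference detectable with 80% power at n = 20 |
|---|---|---|---|---|
| 2 | 0.763 (n = 11) | 12 (0.802) | 0.959 | 2.27 |
| 3 | 0.786 (n = 14) | 15 (0.817) | 0.922 | 2.52 |
| 4 | 0.796 (n = 16) | 17 (0.823) | 0.888 | 2.68 |

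Other patterns need fewer. With four groups, 12 suffice if one group differs from the rest, and 9 if two differ from two. The printed inputs with these defaults therefore do not return 20.

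**What does return 20, or nearly so.** Each of these adds one input that the visible text does not state:

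- Four-group ANOVA with 15% dropout: 17/0.85 = 20.
- Three-group ANOVA with 25% dropout: 15/0.75 = 20.
- Four-group ANOVA at alpha 0.025: 20 (power 0.822). The protocol lists two primary outcome measures, so halving 0.05 would be one reason for that level; the plan does not say this was done.
- Scheffé comparison of a pair among four groups: 20 (0.795 at 19, 0.821 at 20).
- Pairwise t-tests with Bonferroni over the six pairs of arms: 19.
- Counting the later dual-therapy stage as a fifth or sixth group: 18 or 19.

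**If change is analysed between groups.** With SD 2.5 at each visit and correlation ρ, the SD of change is 2.5√(2(1 − ρ)). This equals 2.5 at ρ = 0.5 and 3.54 at ρ = 0.

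| ρ | Power at n = 20: 2 groups | 3 groups | 4 groups |
|---|---|---|---|
| 0 | 0.744 | 0.644 | 0.579 |
| 0.2 | 0.832 | 0.747 | 0.686 |
| 0.3 | 0.878 | 0.805 | 0.750 |
| 0.4 | 0.922 | 0.865 | 0.819 |
| 0.5 | 0.959 | 0.922 | 0.888 |
| 0.7 | 0.998 | 0.993 | 0.988 |

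Power reaches 80% at ρ = 0.129, 0.291 and 0.373 for two, three and four groups. The three- and four-group figures again use the least favourable means.

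**If the pretreatment comparison is within a group.** For a paired t-test with 20 subjects at ρ = 0, the noncentrality is 3/(2.5√2/√20) = 3.79 on 19 degrees of freedom. Power is 0.949, and it rises with ρ (0.990 at 0.3).

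**The case for a change.** The best case for asking for a change is that the mismatch can go either way. On the same printed inputs, four-group power for 3 points is 89% if a single score is analysed and 58% if change is analysed with zero correlation. The sizing sentence attributes 20 to 80% power and to nothing else, and several incompatible routes lead to it. Naming alpha, the contrast, score or change, and any allowance would take one or two sentences.

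Some of this stands. The visible text does not let a reader rebuild the 20, and the arithmetic behind 12, 15 and 17 is sound.

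The rest is weaker. Without a printed alpha, group count or allowance, comparing 20 with 12, 15 or 17 tests the reader's assumptions and not the plan's arithmetic. The arm sizes are blacked out, and a run of blacked-out lines precedes Section 14, where no Section 13 is visible. An allowance may therefore be in the full document.

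The unfavourable case needs three things together: a between-group ANOVA on change, SD 2.5 at both visits, and a low correlation. Section 14 does not say that the ANOVA is on change. Its sentence about pretreatment reads at least as naturally as a within-group comparison, where power is about 95% or more.

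The group count is not truly in doubt either. Four arms are named, and the singular wording occurs in text about follow-up and later dual therapy, not in a definition of the analysis.

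**Conclusion.** The concern does not call for a change. Read as written, with one-way ANOVA on a score whose SD is 2.5, 20 per group delivers more than the stated 80% power: about 96%, 92% and 89% for two, three and four groups. This assumes two-sided alpha 0.05, equal groups, no losses and the least favourable means. If 20 is the enrolled number and 15% are lost, the 17 who remain still give about 82% in the four-group ANOVA.

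What is missing is reporting detail: alpha, comparison, score or change, and any allowance. The ordinary ways of filling it in on a single score either leave 20 conservative or arrive at about 20. Stating the detail would leave the 20 per group as it is and, on that reading, the named analysis too. A null result in this pilot would in any case be judged from the observed differences and their confidence intervals, which rest on the SD found in the data.

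One limit remains. If the trial reports a between-group analysis of change and the pre/post correlation proves to be below about 0.37 with four groups (0.29 with three, 0.13 with two), the 80% claim should not be carried over to that analysis. The documents give no correlation, so they do not show that this will happen.

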#### **10. Potential Risks:**

The risks of radiofrequency, high frequency laser treatment, and dual therapy administering both radiofrequency and a high frequency laser of the vulvovaginal region include discomfort, mild edema, temporary erythema, spot bleeding, potential for transient over-active bladder, injury to bowel and bladder, and painful intercourse due to over-treatment. Less commonly, scarring, burns, and infection could occur. Should infection occur, treatment with antibiotics and even surgical intervention (i.e. I&D) may be required.

The risks of vaginal wall punch biopsy include pain, bleeding, bruising, infection, and possible scarring.

The RF or HFL treatment procedure will be performed by a medical provider who has been trained by [REDACTED] in the application of the device. The punch biopsy and probe application will be performed by this same doctor. There is no known risks associated with the suction probe to measure the anterior biomechanical vaginal wall tissue properties in situ.

There is also a potential risk of Loss of Confidentiality during data collection. However, this risk can be minimized by de-identification of the patient data, and access limited to members of the research team.

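### The primary VSQ comparison has no analysis set and no rule for missing scores, so by default the one-way ANOVA compares only women with a score and may be biased if loss is outcome-related and uneven by arm

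*Combined protocol and SAP*

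**What the plan says.** Section 14 (Biostatistics) is the whole visible statistical plan. It states that "The primary outcome of this study is the VSQ" and gives the group comparison in one sentence: "One way analysis of variance will be used for comparison of groups both for the VSQ and the Q-PCR data". A second sentence covers change over time: "Questionnaire results will be compared by comparing the results at each time point compared to pretreatment assessment". The sample size rests on "We have estimated the standard deviation to be 2.5" and "To detect a difference of 3 points on this measure with 80% power, 20 subjects per group will be required".

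The section does not say at which visit the ANOVA is done, whether women are analysed as randomised, what happens to a woman without a score, or what dropout was allowed for. It carries no redaction marks, so blacked-out text there does not explain the silence. Other sections are heavily redacted. The claim is therefore only that the visible plan has no such rule.

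Three other places bear on the point:
- Section 4, Treatment Groups: each arm has a three-part treatment or placebo, with follow-up to 6 months. After that, "Those in the placebo group will be provided 3 monthly treatments with both" RF and HFL.
- Section 10, Potential Risks: the energy treatments carry risks that include "injury to bowel and bladder, and painful intercourse due to over-treatment", with scarring, burns and infection described as less common. No rates are given.
- Section 7: women who cannot commit to appointments for a year are excluded. This screens at entry only.

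**The concern.** A one-way ANOVA on observed scores leaves out any randomised woman without a VSQ, and the comparison with pretreatment has the same gap. Randomisation protects the comparison of everyone assigned, not of those who happen to return. If women who do badly leave one arm more than the other, the remaining means differ even when the treatments do not.

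Two features of this trial could make loss uneven. The risks of the energy treatments would fall mainly on the active arms, and placebo women may stay because active therapy follows. Both would favour the device. The stated hypothesis in Section 1 is that any benefit may be a placebo effect, so a spurious device effect would undermine the question being asked. In arms of about 20, two or three losses are enough to matter.

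**Working it through.** **Inputs.** From Section 14: SD 2.5, target difference 3 points, power 80%, 20 per group. Assumed because the documents do not give them: two-sided 5% error, equal groups, and every loss rate and loss pattern below.

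**Step 1: the plan's own figure.** The usual formula is n = 2(1.96 + 0.84)² × SD² / difference² = 2 × 7.84 × 6.25 / 9 = 10.9, so 11 per group. The exact t test needs 12. A four-group ANOVA with two means 3 points apart and the others midway needs 17. The stated 20 is not reproduced from the stated inputs, but it exceeds all of these and so is not shown to be wrong. Power at 20 per group is about 96% (t test) or 89% (that ANOVA). With 16 completers per group it is about 91% or 80%. The sample size can absorb some loss of power, so the issue is bias.

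**Step 2: worst-scoring women lost from one arm only.** With no true effect, removing the k worst of 20 shifts that arm's mean by SD × (sum of the k largest expected normal order statistics) / (20 − k). For n = 20 the three largest are 1.867, 1.408 and 1.131 SD.
- k = 1: 2.5 × 1.867 / 19 = 0.25
- k = 2: 2.5 × 3.275 / 18 = 0.45
- k = 3: 2.5 × 4.406 / 17 = 0.65

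Simulation of the two-arm test gives the same shifts and two-sided error of 6.9%, 10.4% and 14.6%, against 5% with no loss. If the active arm loses these women, the shift favours the device. If the placebo arm loses them, the size is the same and the sign is opposite. When both active arms in a four-arm ANOVA each lose k women, error is 7.3%, 11.5% and 17.1%.

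**Step 3: loss that becomes more likely as the score worsens.** Dropout is simulated by a probit rule with slope 2 per SD, with 20 per arm and no true effect. The chance of a false claim for the device is nominally 2.5%.

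| Loss, active / placebo | Bias (positive favours device) | False claim for device |
|---|---|---|
| 20% / 0% | +0.78 | 14.9% |
| 30% / 10% | +0.66 | 13.6% |
| 20% / 10% | +0.36 | 6.5% |
| 20% / 20% | 0.00 | 2.3% |
| 10% / 20% | −0.33 | 0.8% |
| 0% / 20% | −0.78 | 0.3% |

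The first row can be checked by hand: 2.5 × (2/√5) × 0.280 / 0.80 = 0.78, where 0.280 is the normal density at the 20% point.

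**Step 4: what a better model recovers.** If loss depends on an earlier VSQ that was observed, the completers' bias of 0.30 falls to about 0 under a model using all values (assumed correlation 0.5). If loss depends on the unseen final score, most of the bias stays: about 0.43 of 0.62 at correlation 0.5. With baseline as the only earlier value and three women lost, about 0.59, 0.51 or 0.35 of 0.64 remains at correlations 0.3, 0.5 and 0.7. Giving the three missing women the placebo mean leaves 0.65 × 17/20 = 0.55, and a single imputed value understates the variance.

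**The case against.** A reader might infer that the analysis is bound to tilt toward the device. The documents do not support that. They give no dropout by arm, and Step 3 shows that the sign depends on which arm loses women with worse scores.

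The two reasons for expecting active-arm loss are also weaker than they look. The later dual therapy holds placebo women selectively only if they know or guess their allocation. Blinding and the timing of disclosure are not visible in the redacted text. Under blinding, an unhelped woman on active treatment might stay too, hoping that she had placebo. The risks in Section 10 have no rates, some are described as less common, and the biopsy risks may fall on all arms.

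It is also too strong to say that ANOVA can use only observed scores, since it does not forbid imputation. The fault is that the plan is silent. Nor does Section 14 tie the ANOVA to a visit, so a per-visit analysis is a reading of the text.

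Finally, this is a self-described pilot, it screens for commitment to appointments, it says statisticians will continue to be consulted, and the Step 2 shift of 0.65 is 0.65/3 = 22% of the target difference.

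The points about direction and about imputation stand, and they limit the claim. The others do not remove it. Entry screening does not deal with a score that later goes missing. Continued consultation is not a pre-specified rule. Bias of either sign needs one.

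**Conclusion.** The concern holds as a gap in the plan. The primary comparison has no stated analysis set or missing-score rule, so by default it compares women who have a VSQ, and it may be biased if loss is related to outcome and uneven by arm. Bias toward the device is plausible but not established. Under the assumed patterns the bias runs from +0.78 to −0.78 points against a 3-point target, with about no net bias when loss is equal and there is no true effect. With one to three worst-scoring women lost from the active arm, two-sided 5% error rises to about 7 to 15%. These are illustrations that rest on 20 per arm, SD 2.5, normal scores and assumed loss. The documents give no loss rates from which a single figure could be derived. The point is worth correcting because the change is cheap and remote collection has to be arranged before visits are missed.

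**What to change.** In Section 14:
- State that all randomised women are analysed in their assigned arm.
- Replace the one-way ANOVA for the VSQ with a mixed model for repeated measures on all VSQ values from baseline to 6 months (arm, visit, arm by visit). Make the active-versus-placebo contrast at 6 months the primary comparison, because placebo women receive active therapy after that.
- Report loss and its reasons by arm.
- Add a multiple-imputation sensitivity analysis that makes missing scores progressively worse, separately in each arm, to show how far the conclusion depends on them. Single imputation of the placebo mean is not an adequate substitute (Step 4).

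In the study procedures, obtain the 6-month VSQ by telephone or mail from women who stop treatment or miss the visit. This is the main protection, because the model corrects only for loss explained by scores already observed.

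The cost is some SAP wording, a mailed form or telephone script, and slightly more analysis and follow-up work. The estimated effect may also be smaller.
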